Data Sources. **Table 1** summarizes constituent components of utilization and cost and their corresponding data sources. Components are divided by whether they will be used to measure costs for active rTMS only (Tx Group = Active) or for both sham and active rTMS (Tx Group = Both). Health care utilization will be determined from national VA data systems, patient responses recorded on study forms, and study case report forms (adverse events, in particular). Cost estimates will be derived from national VA data systems, published sources, and accounting values provided by VA administrators.

We will use centralized VA databases to obtain the health care services used by the trial participants. From the database of VA inpatient hospital stays, the Patient Treatment File (PTF), we will obtain the date of discharge, days of stay in each ward (bedsection), including the number of days in intensive care, and the ICD-9 diagnoses (up to 10 codes) assigned to the stay. Then, we will obtain from the outpatient care file (OPC), the date of the visit, the location of care (stop code), and ICD-9 diagnoses (up to ten) and CPT codes (up to five) assigned to describe the visit and the type of provider. All major types of outpatient care are captured, including mental health and substance abuse as well as general medical services utilization. The cost of other care (including diagnostic tests) will be obtained from detailed utilization data, which is available from centralized VA Austin databases. National VA utilization databases (PTF and OPC) lack cost estimates, but they can be merged to the Health Economics Resource Center (HERC) average cost database, and accepted methods applied.

Table 1. Resource Utilization and Associated Costs

Tx Phase/Resource Category	Tx Group	Primary Source(s) and Notes
Pre-screening for patient safety	Active	Case report forms and provider wage rates
Treatment for rTMS-related adverse medical events	Active	Adverse events reporting forms, OPC and PTF, and administrative HERC files. We will link study data on adverse events with administrative data on services utilization and costs.
rTMS device and associated physical equipment costs	Active	Equipment prices will be obtained from study investigators. Average per session expense will be imputed using straight-line depreciation plus rental cost, with per session costs distributed across the equipment's useful lifetime.

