Staff time during rTMS sessions	Active	Case report forms and provider wage rates
Staff time for planning ongoing rTMS care and for post-treatment services	Active	Provider reports
rTMS-related non-clinical administrative staff time	Active	Administrative staff reports
rTMS-related medical supplies	Active	Study investigators and administrative staff
rTMS-related electricity expense and other overhead	Active	Study investigators and administrative staff
Office space for rTMS sessions	Active	Study investigators and administrative staff. Imputed rental cost.
rTMS-related computer resource use	Active	Study investigators and administrative staff
Inpatient stays	Both	VA administrative HERC cost files
All non-rTMS outpatient visits	Both	VA administrative HERC cost files
Prescription medication	Both	DSS pharmacy extracts and Pharmacy Benefits Management (PBM) data.

Comparison of HERC & DSS Costs. Data from the VA administrative HERC average cost data files will be used to estimate most outpatient and inpatient costs.¹²⁻¹⁵ The HERC average cost data provide cost estimates; the true cost is unknown. For a second set of cost estimates, we will use the VA Decision Support System (DSS). DSS is a detailed cost allocation system that was implemented in 1997 across the VA. Although DSS is a sophisticated accounting tool that taps VA cost and utilization databases for “real time” managers’ use, its use by researchers is limited. Ongoing validation studies with DSS data show that the cost estimates need to be carefully reviewed to find administrative errors. Because DSS is not standardized nationally, we will use DSS as a secondary source of cost and utilization data in a sensitivity analysis. Recent research compared the HERC and DSS

cost estimates, and the research provides guidance on how to use DSS to test the sensitivity of the HERC data.¹⁶

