Pharmacy Costs. The cost of outpatient prescription medications will come primarily from the DSS Pharmacy Extract. The DSS Pharmacy Extract is a relatively new data source that now covers all VA health care systems and medical centers. The DSS cost includes the medication and a dispensing fee that reflects labor and supply costs for the source of the prescription, either the VA study sites or the VA centralized mail order pharmacy. Preliminary analysis by VIREC suggests that these data are quite comparable to the VA Pharmacy Benefits Management (PBM) data, except that the PBM cost estimate does not include a dispensing fee. To verify the completeness and accuracy of DSS prescription records and associated costs, we will also access prescription data from the PBM database and compare them to DSS data. PBM prescription records could be more complete and accurate in some respects, particularly for inpatient stays. DSS inpatient pharmacy records have been aggregated; they contain one cost amount per day rather than separate records for each prescription. Also, we will compare PBM to DSS for reporting of diagnostic tests, which could be under-reported in DSS. Finally, we will compare the DSS pharmacy data with the study records on the dispensing of any medications to make sure that no double counting occurs.

2. *Identification of rTMS Intervention Costs*

The cost of the rTMS intervention will be estimated by aggregating the costs of component services and physical resources. Services costs will be derived from data on provider type, service type, and service duration using standard methods. Providers' nominal earnings will be multiplied by a loading factor (>1) to adjust for fringe benefit and overhead costs. Costs will be assigned to all physical resources, including donated office space and computer time, using standard resource valuation methods. The cost of physical resources (e.g., rTMS devices) will include depreciation costs plus the rental cost of capital. Resource prices will be obtained from published sources or will be obtained from VA administrators or resource suppliers.

3. *rTMS Cost Consequences*

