We will estimate the average cost differences between active-rTMS and usual care during the acute treatment phase and the follow-up phase. Two analyses will be conducted, one for the period extending 24-weeks post-treatment and one for the period extending 6- to 12-months post-treatment. Total average direct and indirect health care costs for all inpatient and outpatient care will be included in our estimates. Will also produce separate estimates by study phase (treatment or follow-up), in order to isolate any post-treatment cost-offset effects. We will

collect utilization and cost data from HERC, DSS Pharmacy, PBM, and National Patient Care Database (OPC and PTF) files for at least a 30-month period, starting one year prior to the date of randomization and extending one year after the end of the treatment follow-up phase. For patients randomized to sham-rTMS, we will assume that health care utilization and costs during the post-treatment phase are representative of usual health care utilization and costs for these patients. An imputation approach (described in the next paragraph) will be used to estimate their cost of usual care during the acute treatment phase.

Usual Care Costs for Patients Randomized to Sham rTMS. As noted earlier, usual daily cost values will be imputed for patients in the comparison group. Imputation is necessary because our cost analysis requires an estimate of the difference between the cost of providing rTMS intervention and the cost of providing “usual services over a similar period of potential intervention time”. This “incremental cost” cannot be estimated by the difference in average health care costs during the acute treatment phase between the active- and sham-rTMS treatment groups. The estimator for the average incremental cost of rTMS can be expressed as $E(C | T_a) - E(C | T_u)$, where C is health care cost, T_a indicates receipt of active rTMS and T_u indicates receipt of usual care. In randomized trials, estimates of the second component of this expression, $E(C | T_u)$, are normally calculated as the average cost of care in the comparison group. In this trial that approach is problematic, because this trial will not include a “usual care” group, and the sham-rTMS group will potentially get protocol-driven additional days of care as compared to the active-rTMS group, if the latter is more effective.

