Instead, we propose to estimate the cost of usual care for the sham-rTMS group during the pre-intervention acute treatment phase using HERC estimates of all (inpatient and outpatient) VA health care costs during the 6-month period immediately preceding the date of study recruitment. Using these cost estimates, we will calculate each patient’s *average estimated daily health care cost*. We will multiply these estimated daily cost values by the average duration (in days) of the acute treatment phase, measured from first to last day of rTMS therapy, among patients randomized to active-rTMS. The average duration represents the expected number of days of usual care that essentially will be foregone as a result of receiving active-rTMS. The product of the average daily health care cost value and the average duration will be our imputed value for the usual cost of care in the sham-rTMS treatment group during the acute treatment phase of the trial.

Mortality. Mortality information is potentially significant to this economic study because of the potential for patients who die to have very high health care costs just prior to expiring. Deaths will be identified by searching the VA Patient Treatment File and the VA Beneficiary

Identification and Record Locator System (BIRLS) death file. In sensitivity analyses, all analytical findings will be replicated leaving patients who died during the treatment or follow-up periods out of the analytical sample. The resulting estimates will be compared with results from the complete sample and any differences will be noted in our reporting of the research findings.

Inflation and Discounting. Dollar amounts in the study will be presented in terms of the price level as of the last year of data collection. We will adjust costs for inflation using the Consumer Price Index (CPI) for all urban consumers and all goods, the most common measure of nationwide inflation. The CPI is calculated on the basis of a basket of 305 items representing all goods and services purchased for everyday living by all urban residents. We will follow standard discounting methods, and discount health benefits and expenditures at a rate of 3% per year.¹ As noted earlier, HERC cost estimates are adjusted for regional differences in health care labor costs.

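### The imputed usual-care cost for the acute phase uses HERC inpatient and outpatient costs only, so it omits at least the outpatient prescription costs that Table 1 assigns to both groups

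*Protocol*

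**What the plan says.** The trial has no usual-care arm, so Appendix M imputes one for the acute phase. Section D.3 (Usual Care Costs for Patients Randomized to Sham rTMS) does this in three steps:

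- The cost base is obtained "using HERC estimates of all (inpatient and outpatient) VA health care costs during the 6-month period immediately preceding the date of study recruitment".
- A daily value is derived from that base and nothing else: "Using these cost estimates, we will calculate each patient’s" average daily cost.
- The daily value is scaled up: "We will multiply these estimated daily cost values by the average duration (in days) of the acute treatment phase" in the active arm.

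Prescriptions are handled elsewhere. Table 1 gives prescription medication its own row, separate from the inpatient and outpatient visit rows that use HERC. It marks the row as applying to both groups and names the source as "DSS pharmacy extracts and Pharmacy Benefits Management (PBM) data". Section D.1 (Pharmacy Costs) agrees: "The cost of outpatient prescription medications will come primarily from the DSS Pharmacy Extract". D.1 describes the HERC files more narrowly, as data that "will be used to estimate most outpatient and inpatient costs".

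Section D.4 defines the numerator of the incremental cost-effectiveness ratio (ICER) as the between-group difference in average acute treatment cost. Section A adds the imputed acute-phase cost to actual follow-up costs to form the comparator's total.

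**The concern.** A cost comparison needs the same components on both sides. Under Table 1 the active arm's acute phase carries rTMS, inpatient, outpatient and prescription costs. The D.3 formula gives the comparator's acute phase inpatient and outpatient costs only. These prescription costs do arise in the active arm: Appendix G (Risk Minimization, item 5) has patients stay on their medication, apart from drugs that raise seizure risk. Section B also lists lower psychotropic drug use among the possible offsets, so the plan itself treats drug cost as relevant.

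The acute-phase contrast is the ICER numerator and one part of the totals in cost hypotheses 1 and 2. A component missing from one side shifts all of these in the same direction, and a larger sample does not reduce the shift. The bootstrap region in D.4 describes sampling error and would not reveal it.

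**Working it through.** The protocol gives no figure for the imputed cost, the prescription cost or the ICER, so there is nothing to reproduce. The direction follows from the estimator itself.

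**Direction.** Let h be the comparator's daily HERC cost, r its daily prescription cost not contained in HERC, D the active arm's mean acute-phase duration in days, and C_a the active arm's acute-phase cost with all Table 1 components.

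- As written: E(C|Tu) = h × D, so the incremental cost is C_a − h × D.
- With the Table 1 components: E(C|Tu) = (h + r) × D, so the incremental cost is C_a − (h + r) × D.
- Difference: r × D. For any r > 0 the written formula gives the larger incremental cost.
- With a positive remission difference Δ, the ICER is too high by r × D / Δ.

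**Size, as an illustration only.** Inputs:

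- Annual VA cost per depression patient: $5,535 (Appendix M, C.2, FY02).
- A higher value for treatment-resistant patients: 2 × $5,535 = $11,070. C.2 gives a ratio of at least 2 against non-resistant patients; applying it to $5,535 is an assumption.
- Acute phase: 4 to 11 weeks, or 28 to 77 days (Appendix M, A).
- Prescription share of total cost: 10% to 30%. This is an assumption; the documents give no share.

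Formula: r × D = share × annual cost / 365.25 × D.

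| Annual cost | D (days) | Full usual-care cost | 10% | 20% | 30% |
|---|---|---|---|---|---|
| $5,535 | 28 | $424 | $42 | $85 | $127 |
| $5,535 | 77 | $1,167 | $117 | $233 | $350 |
| $11,070 | 28 | $849 | $85 | $170 | $255 |
| $11,070 | 77 | $2,334 | $233 | $467 | $700 |

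The ends of this range are extreme, because D is an average and 28 and 77 days are limits for individual patients. Under Appendix K, section 3, six blocks of at most 12 calendar days come to 6 × 12 = 72 days if run back to back. The top value would then be 0.30 × 11,070 / 365.25 × 72 = $655. At six weeks (42 days) the range is 0.10 × 5,535 / 365.25 × 42 = $64 to 0.30 × 11,070 / 365.25 × 42 = $382.

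**Effect on the ICER.** Each $100 omitted per patient adds $100 / Δ. Appendix G cites a meta-analysis with remission of 9% against 6%. At that 3-point difference the addition is 100 / 0.03 = $3,333 per remission; at an assumed 15 points it is 100 / 0.15 = $667. The 3-point figure comes from that meta-analysis and is not stated as this trial's own assumption.

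**The case against.** The best defence is that D.3 names its sources incompletely and does not choose to leave drugs out. Table 1 marks prescriptions for both groups, so it governs the comparator as much as the active arm. D.3 plans to "collect utilization and cost data from HERC, DSS Pharmacy, PBM, and National Patient Care Database (OPC and PTF) files for at least a 30-month period". That window opens a year before randomization, so pre-period pharmacy data will be at hand. Section F.2 has prior-year expenditure calculated in both study groups. D.3 also describes the costs of both arms as covering all inpatient and outpatient care, the same scope as in the imputation sentence. If that wording includes drugs in one place, it can be said to include them in the other.

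Most of this stands as evidence of intent: drugs were probably meant to count in both arms. It does not repair the formula. The imputation sentence names HERC as its only source, the daily value is built from those estimates alone, and no sentence adds DSS or PBM costs to it. Reading drugs out of both arms would equalise the components, but it would contradict Table 1. Either way the two places need reconciling.

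It can also be said that section D.5 compares the imputed costs with those of similar non-participants and carries the resulting ranges into the results. That is a check on the level of the imputed cost, but it does not mention pharmacy and need not expose a missing component.

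**Conclusion.** The point holds as an inconsistency between an explicit formula and the plan's own list of cost components. As written, the comparator's acute-phase cost omits at least outpatient prescriptions, and the acute-phase incremental cost and ICER numerator are too high by r × D. Hypotheses 1 and 2 are affected only through the acute phase, because the sham group's follow-up costs are actual costs.

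A reader might infer more than the documents support:

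- **That all acute-phase drug cost is missing.** The protocol does not say whether HERC inpatient averages already contain inpatient drugs, so only the outpatient part is secure.
- **That usual care is understated by 10% to 30%, or the ICER by some given amount.** The percentage merely restates the assumed share, and the dollar figures depend on it and on the chosen duration and remission difference. The size cannot be fixed from the documents.
- **That the economic comparison as a whole is biased against rTMS.** Other features of the imputation, such as unusually high service use before recruitment, could push the other way. The net bias is not settled here.

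The clinical efficacy analysis is not touched.

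**What to change.** In Appendix M, D.3, define each sham patient's pre-period daily cost as HERC inpatient plus HERC outpatient plus DSS Pharmacy outpatient prescription cost over the same six months, with PBM as the check. Add inpatient drug cost only if the HERC inpatient averages are confirmed not to contain it, and apply the same rule to the active arm. State that the imputed cost must cover every Table 1 row marked for both groups.

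The cost is a few lines of text and one check on what HERC inpatient averages include. No new data are needed, since the required pharmacy files are already to be extracted for the year before randomization.

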11. Was the rTMS treatment completed? No Yes
12. If No, specify the primary reason using the codes (see last page for codes) _____
13. rTMS administrator's initials: _____

CODES:

1 = Equipment malfunction	4 = Adverse Device Event/Adverse Event
2 = Participant refused	5 = Unanticipated Adverse Device Event/Serious Adverse Event
3 = Staff error	6 = Other, specify _____

VA COOPERATIVE STUDY #556
The Effectiveness of rTMS in Depressed VA Patients

Site ____ Participant # _____ Alpha Code _____ Date ___/___/___- MM / DD / YYYY

Form 20 – HRSD and MADRS

Circle Visit Below:

Screening

Acute Treatment Phase Sessions: 5 10 15 20 25 30

Follow-up Phase Weeks: 4 8 12 16 20 24

Interviewer's Initials:	_____		
Start Time:	_____ (24 hour clock)		
MANUAL SCORING INSTRUCTIONS: Write the score of the item in the box for the 24 HRSD items. Take the sum of these values and write it in the Total HRSD Score box at the end of the form.			
Introductory Questions: "I'd like to ask you some questions about the past week. Since last (DAY OF THE WEEK), how have you been feeling? Have you noticed any change in how you have been feeling during the past week compared to before?"			
Interview Guide	HRSD Scoring Criteria	MADRS Scoring Criteria	
SLEEP (Early and Middle Insomnia)			
"Let's talk about your sleep. During the past week, what were your usual hours of going to sleep and waking up? How many hours of sleep at night would be best for you?" If patient had a significant period of euthymia in past 5 years: "How many hours of sleep did you get when you were not depressed and feeling well?"			
"Have you had any trouble this week falling asleep at the beginning of the night?" After you have gone to bed, how long has it been taking you to fall asleep? How many nights this week have you had trouble falling asleep?	H4. INSOMNIA – EARLY  (0) Less than or equal to 1/2 hr to fall asleep (always add a point for use of a hypnotic at bedtime)  (1) Greater than 1/2 hr at least 2 days and less than 5 nights in the past week  (2) Greater than 1/2 hr 5 or more nights in the past week		

Interview Guide	HRSD Scoring Criteria	MADRS Scoring Criteria

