- 4) Assessments required in the protocol, including substance abuse and suicidality, etc are summarized on page 37 of the submitted protocol and discussed in the subsequent pages of the protocol.
- 5) Suicidality Risk Minimization - A common practice is to stop a treatment if a patient makes a suicide attempt. Because this may occur early in treatment, before a patient is adequately treated (in the active group), we would elect to continue treatment with the patient in an inpatient unit if the patient agrees to continue the trial. Discharge would be based on the patient's ability to adhere to a modified safety plan (listing behaviors and strategies in the event of increasing suicidal impulses, including returning to the ER). We will develop a safety plan agreed upon with the clinician and the patient as a condition of entry into the study. Failure of the patient to comply with the safety plan will require stopping study treatments and aggressively treating the suicidality.

As a condition of participation, we will insist that those patients with a history of suicidality have all firearms either removed from their residence or placed under lock and key, including trigger locks, with guns and ammunition locked separately and the keys given to another family member or friend. Suicide is an impulsive act and since our patients know how to use firearms effectively, the decision to make a suicide attempt will more likely be fatal if a firearm is available. Thus, another stopping point will be a violation of the firearms agreement and/or the procurement of a new firearm during the study.

Another way we are attempting to decrease the suicide risk to the patient is to enable the patient to continue in treatment with his/her outpatient clinician and to continue taking all medication except those which would convey an increased risk of seizures (which would likely have resulted in the patient's having been excluded). Should the patient drop out of outpatient treatment or if we receive information from the clinician that the patient is imminently suicidal, we will institute appropriate safety measures and discontinue study treatments if a major change in medication or treatment is necessary. Similarly, any patient who is so imminently suicidal (or homicidal) that he would require involuntary treatment, would no longer meet criteria for continuing study treatments.

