 - Patient should be routinely queried at each visit as to whether they have experienced any adverse events. Reports of significant, possible related adverse events such as changes in hearing or vision should prompt adverse event reporting and further evaluation to ensure that no patient is placed at excessive risk.

5. *Interruptions*

Every attempt shall be made to complete each treatment session as per the protocol. Interruptions during the treatment are allowed as needed for patient comfort or convenience by using the “pause” selection on the device. However, in the event that an incomplete treatment is given, this information will be recorded. Total number of treatments will be recorded. Since this is an “intent to treat” design, patients that miss treatments are not removed from the study. However, post-hoc analyses will examine the effects of compliance on overall outcome.

6. *Evaluations*

Patients are first tested for “remission” after the first 20 sessions of treatment and then again at the 25th and 30th sessions. Remission is defined as a decrease in Hamilton Rating Scale for Depression *to 10 or less*. If a patient enters “remission” after 20 sessions, then they enter a 24-week follow-up period. If a patient does not enter “remission” at the end of 20 sessions, they are offered an additional 5 sessions of treatment and retested for “remission.” This procedure may continue for a

maximum of 10 additional sessions resulting in a total of 30 sessions. Patients who do not show a treatment response at the end of 30 sessions of treatment or who drop out during treatment will be considered a treatment “failure”.

At the end of the acute treatment phase, all patients will be entered into a 24 week follow-up phase. Participants who remit will receive a 3 week treatment taper at the beginning of the follow-up phase. The taper will include 3 treatment sessions in the first week, 2 in the second week and 1 in the last week of the taper.

7. *Sham (Control) rTMS Treatment*

Sham (Control) treatment will be accomplished by using the Cool-B65-A/P coil that functions both as an active (A) and placebo (P) coil. It has a symmetrical mechanical design and no labeling on the coil indicates the active or placebo side. Consequently it is not possible for the operator to see or hear which side is used.

8. *Masking*

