The short-term 24-week period was chosen to coincide with the collection of clinical endpoints at the end of the CSP 556 follow-up phase. The longer term 6- to 12-month period was chosen to maximize the opportunity to observe cost offsets from rTMS. The reason for specifying 6- to 12-months rather than a single time period is that due to extant data lags we do not know in advance how long of a retrospective period will be available to us, given the potential variability in the timing of patient recruitment. Maximization of sample size is paramount to accurate cost estimation. Therefore, we will select the longest 6- to 12-month post-treatment period that will allow us to include the largest sample of study participants. We believe that nearly all patients will have completed treatment and will have 6-months post-treatment cost data available before the end of the three-year study. A longer cost consequence follow-up will be pursued, if the extant data are available. Cost consequences

results will be discussed in terms of statistical significance and the magnitude and types of differences (e.g., inpatient and outpatient).

We will then estimate the cost-effectiveness of rTMS therapy in producing a sustained remission from depression (HRSD \leq 10) at 24-weeks post-treatment. We will report the incremental cost of rTMS per incremental remission, which will provide a standardized measure of the cost-effectiveness of rTMS therapy relative to that of “usual outpatient care”. These estimates will allow us to test a third hypothesis:

3. Relative to usual care, rTMS therapy for treatment-resistant depression is cost-effective in producing a sustained remission from acute depressive symptoms, in outpatients.

We will calculate a 95% confidence region for all estimated cost-effectiveness ratios. The ratios will be discussed in light of the cost-effectiveness of antidepressant medication and ECT. Estimates for these alternative therapies are available from published studies.^{3, 4}

C. Background

1. Prevalence

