The remission outcomes data – where a sustained remission is defined as HRSD \leq 10 at 6-weeks post-treatment – will be used in conjunction with incremental treatment cost estimates to determine an incremental cost-effectiveness ratio (ICER) for the intervention. The resulting ICER will represent the estimated incremental cost per sustained remission, measured at 6-weeks post-treatment. The ratio will be expressed as: $ICER = [E(C | T_a) - E(C | T_u)] / [P(R | T_a) - P(R | T_u)]$, the difference in average acute treatment costs divided by the difference in probability of remission (R) between the two groups. Note that this assumes that the P(R) among patients receiving sham-rTMS is approximately equal to the probability of remission among usual care patients. A 95% confidence region surrounding cost-effectiveness ratios will be estimated using bootstrapping methods.¹⁷⁻¹⁹

The cost-effectiveness analysis could produce one of three major results: (1) rTMS may be cost neutral or less expensive and also more effective than usual depression care, indicating that its implementation is highly desirable; (2) rTMS might not be shown clinically effective in the VA, in which case its relative cost impact is irrelevant to VA decision-makers; (3) rTMS therapy will be more expensive than sham but will yield a greater likelihood of sustained remission. In this last case, the costs of a sustained remission will be compared with the cost of the main alternative treatment option, namely ECT. Estimates of ECT costs will be derived from the literature and from VA administrative sources.⁴

5. Sensitivity Analyses

We will test the sensitivity of our results to a number of assumptions. At a minimum, we expect them to include:

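### Hypothesis 3 and the ICER claim a sustained remission, but Appendix M scores it from a single HRSD reading, so the ratio describes remission at a visit

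*Protocol*

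**What the plan says.** Hypothesis 3 (Appendix M, B. Objectives) is that "rTMS therapy for treatment-resistant depression is cost-effective in producing a sustained remission from acute depressive symptoms, in outpatients". The sentence that leads to it reads "We will then estimate the cost-effectiveness of rTMS therapy in producing a sustained remission from depression" and gives the criterion as HRSD of 10 or less at 24 weeks post-treatment.

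Section D.4 gives the criterion again, "where a sustained remission is defined as HRSD" of 10 or less, but at 6 weeks post-treatment. It adds: "The resulting ICER will represent the estimated incremental cost per sustained remission, measured at 6-weeks post-treatment". The denominator of the ratio is the difference between arms in the probability of remission R. The numerator is described as the difference in average acute treatment costs.

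Appendix K, section 6 tests remission after sessions 20, 25 and 30, and then: "At the end of the acute treatment phase, all patients will be entered into a 24 week follow-up phase". Non-remitters are included. Appendix G (Risk Minimization, item 5) lets patients stay with their own clinician and "to continue taking all medication except those which would convey an increased risk of seizures". Form 16 asks about medication changes from follow-up week 4. The HRSD form (Form 20) is scheduled at acute sessions 5 to 30 and at "Follow-up Phase Weeks: 4 8 12 16 20 24".

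**The concern.** A remission is sustained if it was reached and then held. A single reading shows neither. A cost per sustained remission that is built on one reading answers a different question from the one in hypothesis 3.

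The label matters because D.4 plans to set this cost beside that of ECT if rTMS proves dearer but more effective, and because section B argues that cost offsets build up over time when full remission becomes more likely or recurrence less likely. A VA decision-maker would read the ratio as the price of a lasting result. There is also a mismatch inside the ratio. A remission first reached during follow-up, for example after a medication change, enters the denominator, while follow-up costs lie outside the numerator as described.

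**Working it through.** **What the rule accepts.** Appendix M states no ICER value, sample size or power figure that depends on this definition, so there is no figure to reproduce. The check is to apply the rule to three patient histories:

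- HRSD 10 or less at session 20 and at every later visit: counts.
- HRSD above 10 at sessions 20, 25 and 30, then 10 or less at the scored visit: counts.
- HRSD 10 or less at session 20, above 10 at weeks 8 to 20, then 10 or less at week 24: counts under section B. This history cannot be scored at a 6-week endpoint.

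All three receive the same value of R, and only the first is a sustained remission.

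**The timing and the cut-off also conflict.** Section B says 24 weeks and D.4 says 6. Section B explains that 24 weeks was chosen to match the end of follow-up, so on the same clock 6 weeks is follow-up week 6, and Form 20 has no HRSD in that week. The Overview of Appendix M defines remission as a score below 10, whereas sections B and D.4 say 10 or less.

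**Illustration 1: one step.** End-of-treatment remission p is 9% active and 6% sham, from the meta-analysis of 24 sham-controlled trials summarised in Appendix G. Two inputs are assumed, equal in both arms and not from the documents: 60% of remitters are still in remission at the scored visit (keep), and 5% to 20% of non-remitters score 10 or less there (late).

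Counted rate = p × keep + (1 − p) × late.

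- late = 0.05: active 0.0540 + 0.0455 = 0.0995; sham 0.0360 + 0.0470 = 0.0830; difference 1.65 points.
- late = 0.20: active 0.0540 + 0.1820 = 0.2360; sham 0.0360 + 0.1880 = 0.2240; difference 1.20 points.
- Remitters who persist: 0.03 × 0.60 = 1.80 points.

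Late remissions are 46% to 77% of the active count (0.0455/0.0995; 0.1820/0.2360) and 57% to 84% of the sham count (0.0470/0.0830; 0.1880/0.2240). The ratio of denominators is keep/(keep − late), which runs from 0.60/0.55 = 1.09 to 0.60/0.40 = 1.5. The remission rates cancel, so trying other rates would confirm nothing.

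**Illustration 2: by visit.** A two-state chain in 4-week steps, with relapse r and late remission g per step, again assumed equal in both arms. After k steps the single-reading difference is 0.03 × (1 − r − g)^k and the every-visit difference is 0.03 × (1 − r)^k. With r = 0.10 and g = 0.03:

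| Scored visit | Single reading (points) | Every visit (points) | Ratio ((1 − r)/(1 − r − g))^k | Active patients counted who were in remission throughout |
|---|---|---|---|---|
| Week 4 (k = 1) | 2.61 | 2.70 | 1.03 | 75% |
| Week 8 (k = 2) | 2.27 | 2.43 | 1.07 | 59% |
| Week 24 (k = 6) | 1.30 | 1.59 | 1.23 | 28% |

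At week 24 in this case, the single reading counts 17.0% of the active arm and the every-visit rule 4.8% (0.09 × 0.90^6).

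Over r = 0.05 to 0.20 and g = 0.01 to 0.05, the week-24 ratio runs from (0.95/0.94)^6 = 1.07 to (0.80/0.75)^6 = 1.47. At week 8 it runs from 1.02 to 1.14. The share in remission throughout is 13% to 58% at week 24 and 42% to 82% at week 8. Relapse followed by recovery makes up only 1% to 4% of those counted at week 24. If there is no late remission, the two rules agree.

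**The case against.** The strongest reply is that remission at a fixed visit is a legitimate effect for a payer analysis. The ICER compares rTMS with usual care and lets sham stand in for it. Spontaneous and medication-driven recoveries in the sham arm are what usual care would have produced, and they should be netted off. That part stands. A reader might infer from the illustrations that the ICER is biased or inflated. The documents do not support this: the 1.1- to 1.5-fold factor compares two different effects and comes from assumed inputs.

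A second reply is that Appendix K classes patients without a response after 30 sessions, and those who drop out, as treatment failures, so sustained could be read as a remitter who is still in remission. D.4 does not refer to that rule, and its formula takes the probability of R over each arm. Followed as written, late remissions count.

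A reader might also infer that the trial does not measure durability. That goes too far. Serial HRSD readings are collected, and the main body of the protocol is not among the pages shown, so its clinical durability outcomes cannot be judged. The statement holds only for the effect in hypothesis 3 and the ICER.

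**Conclusion.** The point holds as a mismatch between label and measure. Both definitions in Appendix M give point prevalence of remission, and a cost per such remission cannot support hypothesis 3 as worded. The contrast itself remains valid.

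The size is unknown, because the documents give no late-remission or relapse rates. With rates assumed equal in both arms, the two denominators differ about 1.1- to 1.5-fold at a late endpoint and by at most 1.14-fold at week 8. Late remission drives nearly all of this; relapse followed by recovery adds little. The 9% and 6% starting rates come from trials that mostly followed patients for 1 to 3 weeks and serve only as an illustration.

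This is an economic outcome in an appendix that makes no power claim. It is worth correcting because the correction is cheap and the ratio is meant to inform an investment decision.

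**What to change.** In Appendix M, sections B and D.4:

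1. State one endpoint that falls on a scheduled HRSD visit. This reconciles 6 with 24 weeks. Reconcile the cut-off with the Overview as well.
2. Define sustained remission for hypothesis 3 as remission at the end of acute treatment (session 20, 25 or 30) and at each scheduled HRSD visit up to that endpoint. Add a rule for missed visits, and use this as R.
3. Report the single-visit ICER alongside, labelled remission at endpoint, and say whether follow-up costs enter its numerator. Alternatively, keep the single reading as the effect and remove the word sustained from the hypothesis and the ICER.

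The cost is wording, with no new assessments. There are three downsides. Fewer remissions are counted in both arms. Missed visits need a rule. The stricter definition gives no credit to comparator patients who remit later, which could favour rTMS; this is why both versions should be reported.
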